8.2. Patient Exclusion Criteria

All patients with any of the following conditions or characteristics must be excluded from the study:

1. Participation in other investigational clinical studies involving pharmaceutical products being tested or used in a way different from the approved form or when used for an unapproved indication within 30 days of Day 1;
2. Initiation of an exercise program for cardio-pulmonary rehabilitation within 3 months (90 days) prior to Day 1 or planned initiation during Part 1 of the study;
3. Stopped receiving any PH chronic therapy within 60 days prior to Day 1;
4. Requirement for receipt of intravenous inotropes within 30 days prior to Day 1;
5. Has uncontrolled systemic hypertension as evidenced by sitting systolic blood pressure (BP) > 160 mm Hg or sitting diastolic blood pressure > 100 mm Hg during Screening after a period of rest;
6. Has systolic BP < 90 mm Hg during Screening after a period of rest;
7. WHO Group III patients with pulmonary hypertension primarily associated with chronic obstructive pulmonary disease, sleep-disordered breathing, and/or alveolar hypoventilation disorders;
8. WHO Group III or V patients who at rest require supplemental oxygen at a rate > 4 L/min or have peripheral capillary oxygen saturation (SpO₂) levels < 92%;

9. Has a history of clinically significant left-sided heart disease and/or clinically significant cardiac disease, including but not limited to any of the following:
 - a. Congenital or acquired valvular disease if clinically significant apart from tricuspid valvular insufficiency due to pulmonary hypertension;
 - b. Pericardial constriction;
 - c. Restrictive or congestive cardiomyopathy;
 - d. Left ventricular ejection fraction < 40% per echocardiogram (ECHO) within 60 days of Day 1;
 - e. Any current or prior history of symptomatic coronary disease (prior myocardial infarction, percutaneous coronary intervention, coronary artery bypass graft surgery, or anginal chest pain);
10. Clinical instability within 8 weeks prior to Day 1, such as hospitalization due to respiratory or cardiac symptoms, acutely decompensated heart failure, syncope, or other events that in the investigator's opinion would suggest the patient is an inappropriate candidate for the study;
11. Has more than two of the following clinical risk factors for left ventricular diastolic dysfunction:
 - a. Age > 65 years;
 - b. BMI \geq 30 kg/m²;
 - c. History of systemic hypertension;
 - d. History of type 2 diabetes;
 - e. History of atrial fibrillation;
12. History of atrial septostomy within 180 days prior to Day 1;
13. Obstructive sleep apnea that is untreated;
14. For patients with HIV-associated PAH, any of the following:
 - a. Concomitant active opportunistic infections within 180 days prior to Screening;
 - b. Detectable viral load within 90 days prior to Screening;
 - c. Cluster designation 4 (CD4+) T-cell count < 200 mm³ within 90 days prior to Screening;
 - d. Changes in antiretroviral regimen within 90 days prior to Screening;
 - e. Using inhaled pentamidine;
15. Has a history of portal hypertension or chronic liver disease, including hepatitis B and/or hepatitis C (with evidence of recent infection and/or active virus replication) defined as mild to severe hepatic impairment (Child-Pugh Class A-C);
16. Serum aminotransferase (ALT or AST) levels > 1.5X the upper limit of normal (ULN) at Screening;

17. Hemoglobin (Hgb) concentration < 10.5 g/dL at Screening;
18. Diagnosis of Down syndrome;
19. History of malignancy within 5 years prior to screening, with the exception of localized skin or cervical carcinomas;
20. Active bacterial, fungal, or viral infection, incompatible with the study;
21. Known or suspected active drug or alcohol abuse, per Investigator judgment;
22. Major surgery within 30 days prior to Screening or planned to occur during the course of the study;
23. Unwilling to practice methods of birth control (both males who have partners of childbearing potential and females of childbearing potential) during screening, while taking study drug and for at least 30 days after the last dose of study drug is ingested;
24. Women who are pregnant or breastfeeding;
25. Any disability or impairment that would prohibit performance of the 6MWT;
26. Any abnormal laboratory level that, in the opinion of the Investigator, would put the patient at risk by trial enrollment;
27. Patient is, in the opinion of the Investigator, unable to comply with the requirements of the study protocol or is unsuitable for the study for any reason;
28. Known hypersensitivity to any component of the study drug;
29. Unable to communicate or cooperate with the Investigator due to language problems, poor mental development, or impaired cerebral function;
30. Use of intravenous (iv) or subcutaneous (sc) prostacyclin/prostacyclin analogues;
31. Prior exposure to bardoxolone methyl.

8.3. Patient Re-screening

Patients may repeat the screening procedures to qualify for the study with approval from the medical monitor.

8.4. Patient Withdrawal and Discontinuation

Patients have the right to withdraw from the study at any time for any reason, without prejudice to their medical care. The Investigator may discontinue a patient from the study for any of the following reasons:

- Clinical worsening;
- Occurrence of an adverse event or change in medical status that leads the Investigator or Sponsor to be concerned about the patient's welfare;
- Investigator determines the patient is non-compliant with study procedures;
- Females who become pregnant during the study;
- Failure to return for follow-up.

Patients must be withdrawn from the study if any of the following occur.

- ALT or AST > 8X ULN;
- ALT or AST > 5X ULN for 14 days;
- ALT or AST > 3X ULN and (total bilirubin > 2X ULN or INR > 1.5);
- ALT or AST > 3X ULN with the appearance of fatigue, nausea, vomiting, right upper quadrant pain or tenderness, fever, rash, and/or eosinophilia (> 5%);
- Withdrawal of consent;
- Death.

Patients who discontinue from the study will be asked to complete the end-of treatment and follow-up procedures noted in [Table 3](#) or [Table 4](#) and [Table 5](#) or [Table 6](#) depending on which cohort the patient is enrolled in and whether the patient is Part 1 or 2 of the study. Patients who complete the 16 weeks of Part 1 but choose not to participate in Part 2 (the extension period) should complete the follow-up procedures in [Table 3](#) or [Table 4](#) and [Table 5](#) or [Table 6](#). Patients should complete end-of-treatment procedures, including the 6MWT, prior to any adjustments being made to their PAH treatment regimen. Patients who discontinue for elevated transaminase levels should complete the End-of-treatment visit, the Follow-up visit **and** should also be followed per [Section 9.1.2](#) if acceptable levels are not reached at the Follow-up visit.

Every effort should be made to contact patients who do not return for a scheduled visit. The Investigator should inquire about the reason for withdrawal, request the patient return all unused investigational product(s), request the patient return for end-of-treatment and follow-up visits (if applicable), and follow-up with the patient regarding any unresolved AEs. Patients who discontinue participating in the study for any reason may not re-enter the study at any time.

9. TREATMENT OF PATIENTS

9.1. Select Management Guidelines

The following guidelines apply to the management of study participants:

9.1.1. Management of Fluid Status

Specific risk mitigation procedures will be employed to reduce the potential for bardoxolone methyl-induced fluid overload. These procedures include exclusion of patients with any clinically significant renal disease, defined as an eGFR value of < 45 mL/min/1.73 m². To exclude patients with significant cardiac dysfunction, the study will exclude patients with a history of left-sided heart disease. Patients who have evidence of volume overload at baseline, defined as BNP level of > 400 pg/mL, will also be excluded. Laboratory data will also be used to monitor fluid status after randomization.

Additionally, after randomization patients will be closely monitored for rapid weight gain suggestive of fluid overload. Patients will be given a Sponsor-provided scale to use at home to collect and record their weights daily during the first 4 weeks (Cohorts 1 and 2) or 8 weeks (Cohorts 3 and 4) of the treatment period and weekly thereafter. Patients who experience a five-pound (2.3 kilogram) or greater increase in weight since their Day 1 weight during Part 1 and during the first 4 weeks (Cohorts 1 and 2) or 8 weeks (Cohorts 3 and 4) of Part 2 will be instructed to stop taking their study medication immediately and return to the clinic for an unscheduled physical examination and laboratory assessment by the Investigator. Patients may not restart their study medication until the Investigator has completed and documented an assessment of fluid overload.

Investigators should also advise patients to watch for signs and symptoms of fluid overload. Patients should be informed to notify their physicians immediately if they experience swollen feet, chest pain, and shortness of breath with mild exertion or while lying down, or other relevant symptoms. The Investigator should immediately assess symptoms of fluid overload and determine appropriate medical management, as necessary, including whether stopping drug administration is required. At the earliest sign of worsening or new onset peripheral edema or other signs and symptoms of acute volume overload, Investigators will also be expected to determine if changes to a patient's diuretic regimen is needed.

Since placebo patients will be transitioned to active treatment for the extension period (Part 2), and the blind will be maintained, all patients entering the extension will be closely monitored for weight gain just as they were monitored following randomization into the treatment period. Patients will use their Sponsor-provided scale during the first four weeks (Cohorts 1 and 2) or eight weeks (Cohorts 3 and 4) of the extension period and will record their weights daily. As in the treatment period (Part 1), patients will be instructed to stop taking their study medication immediately and return to the clinic for an unscheduled physical examination and laboratory assessment by the Investigator if they experience a five-pound or greater increase in weight since Week 16 (Day 1 of the extension period).

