5.1.2. Fluid Overload

Similar to ERAs in certain patient populations, including bosentan in advanced congestive heart failure and avosentan in advanced CKD, bardoxolone methyl treatment was found to be associated with an increased risk for fluid overload and heart failure hospitalizations in the BEACON trial, which enrolled patients with Stage 4 CKD (eGFR 15-29 mL/min/1.73 m²) and type 2 diabetes. The overall increased risk for fluid overload and heart failure events with bardoxolone methyl appeared to be limited to the first three to four weeks after initiation of treatment. Elevated BNP and prior hospitalization for heart failure were identified as risk factors that contributed to increased risk for these events. The increased risk for these events from bardoxolone methyl treatment had not been observed in six previous CKD studies, which were mostly conducted in patients with Stage 3b CKD (eGFR 30-44 mL/min/1.73 m²), patients with hepatic dysfunction, cancer patients, or healthy volunteers.

Review of admission notes and narrative descriptions for heart failure hospitalizations in BEACON indicates that heart failure in bardoxolone methyl-treated patients was often preceded by rapid fluid weight gain (several kilograms within the first weeks of treatment initiation) and was not associated with acute renal decompensation or acutely reduced left ventricular contractility. Available data from BEACON and other studies suggest that bardoxolone methyl treatment can differentially affect hemodynamic status according to the clinical condition of patients and likely promotes fluid retention in patients with more advanced renal dysfunction and other recognized risk factors associated with heart failure at baseline. This current study will employ risk mitigation procedures to reduce the potential for bardoxolone methyl-induced fluid overload, including exclusion of patients with the identified risk factors and close monitoring for fluid retention within the first month of treatment.

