Cohorts 3 and 4 patients randomized to placebo in study Part 1 will be assigned to 5 mg of bardoxolone methyl, whereas, patients randomized to bardoxolone methyl in study Part 1 will begin study Part 2 (Week 16) at the same dose of bardoxolone methyl as they ended with in study Part 1. All patients in Cohorts 3 and 4 will have the option to up-titrate their dose at the Week 20 visit, and may de-escalate in dose (minimum dose of 2.5 mg) at scheduled or unscheduled visits. Treatment assignment will remain blinded for Cohort 3 and 4 patients through Week 20.

Treatment-compliant patients who have completed Part 2 of the study are eligible to continue receiving bardoxolone methyl through an extended access program (Study 402-C-1602). After Week 32, visits will occur every 24 weeks until bardoxolone methyl is available through the extended access program. Once bardoxolone methyl is available through the extended access program, patients in Part 2 who have completed at least 32 weeks of the study will complete an End of Treatment Visit. The Week 32 visit may be the same as the End of Treatment Visit. Beginning with the Week 32 visit, patients will be seen in the clinic every 24 weeks (i.e., Week 56, Week 80, Week 104, etc.) and receive a 6-month supply of study drug at the appropriate dose.

The Sponsor reserves the right to stop the study for a given cohort if development of bardoxolone methyl is discontinued for any reason, or if the assessment of available data raises concerns about the safety or efficacy of bardoxolone methyl.

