Cohort 3 and 4 patients randomized to placebo in study Part 1 will be assigned to 5 mg of bardoxolone methyl, whereas, patients randomized to bardoxolone methyl in study Part 1 will begin study Part 2 (Week 16) at the same dose of bardoxolone methyl as they ended with in study Part 1. All patients in Cohorts 3 and 4 will have the option to up-titrate their dose at the Week 20 visit, and may de-escalate in dose at scheduled or unscheduled visits. Treatment assignment will remain blinded for Cohort 3 and 4 patients through Week 20. Dose escalation during the extension period is permitted for all patients at the Week 20 visit only.

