^a Total screening period should not exceed 60 days. If screening is longer than 28 days, BNP should be repeated through the central lab prior to randomization.

^b Study Day 1 is the day of administration of the first dose. **On Study Day 1, all procedures should be performed before study drug administration.**

^c Under the delegation of the Investigator and following Sponsor prior approval for each visit, a patient may be seen by a home health professional, qualified by documented training to perform study-specific procedures. If the visit is completed by home health professional, a limited physical assessment directed to assess for fluid retention and clinical worsening will be performed under the delegation of the Investigator

^d Patients who discontinue from the study prior to the Week 16 study visit will need to be brought back for all early termination assessments (i.e., both an end-of-treatment visit and then a follow-up visit 4 weeks after the date of administration of the last dose of study drug). Patients should complete the end-of-treatment procedures, including the 6MWT, prior to any adjustments being made to their PAH treatment regimen.

^e Screen A eligibility procedures do not need to be repeated on Day 1; however, a review of any changes in eligibility criteria should be evaluated prior to Day 1 procedures, and a urine pregnancy test should be performed for WOCBP.

- ^f Weights taken at home by the patient will begin on Day 2 and should be taken daily for the first 8 weeks and weekly thereafter, preferably at the same time each day and must be recorded in a diary and reviewed with the coordinator during telephone contacts and office visits.
- ^g If clinical worsening is suspected, further clinical evaluations may be required per Section 9.10.32.
- ^h A serum pregnancy test will be performed at Screen A for WOCBP or at any point in time if a pregnancy is suspected. All other pregnancy assessments will be urine pregnancy tests. Additional pregnancy assessments will be performed more frequently if required by local law or requested by local regulatory authorities or IRBs/ECs.
- ⁱ AE assessments on Day 1 should be done following study drug administration.

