Functional class assessment ^l										X		X	X
PK samples ^m					X								
Pulmonary Function Testing	X				X					X		X	X
██████████	█				█					█		█	█

^a All other Week 16 assessments will be completed as per Table 3 or Table 4.

^b Under delegation of the Investigator and with prior Sponsor approval, a patient may be seen by a home health professional. The home health professional must have documented study-specific training on file prior to the performance of any study-related procedures.

^c Visits beyond Week 32 will only occur until bardoxolone methyl is available through the extended access program. Once bardoxolone methyl is available through the extended access program, patients in Part 2 who have completed at least 32 weeks of the study will complete an End of Treatment Visit. If bardoxolone methyl is available through the extended access program prior to Week 32, the End of Treatment visit may coincide with the Week 32 visit.

^d Patients who are discontinued from the study during the extension period for any reason, including Sponsor termination of the study, and patients who are not participating in the extended access program must complete all end-of-treatment and follow-up visit assessments. Patients should complete the end-of-treatment assessments, including the 6MWT, prior to any adjustments being made to their PAH-specific treatment regimen.

- e Weights taken at home by the patient should be taken daily starting at week 16 through and including week 20 and weekly thereafter, preferably at the same time each day and must be recorded in a diary and reviewed with the coordinator during telephone contacts and office visits.
- f If clinical worsening is suspected, further clinical evaluations may be required per Section 9.10.32.
- g A limited physical assessment directed to assess for fluid retention and clinical worsening may be performed by a home health professional under the delegation of the Investigator and with prior Sponsor approval.
- h A serum pregnancy test will be performed at Screen A for WOCBP or at any point in time if a pregnancy is suspected. All other pregnancy assessments will be urine pregnancy tests. Additional pregnancy assessments will be performed more frequently if required by local law or requested by local regulatory authorities or IRBs/ECs.

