9.10.8. Weight and Body Mass Index (BMI)

Weight should be measured at the times indicated in [Table 3](#) or [Table 4](#) and [Table 5](#) or [Table 6](#). Body mass index (BMI) will be calculated in the eCRF each time the weight is recorded. The Sponsor will provide each patient with a scale to use at home to capture daily weights. Weights should be taken at the same time each day and recorded in a patient diary. During the first four weeks (Cohort 1 and 2) or first eight weeks (Cohort 3 and 4) of both Part 1 and Part 2, weights will be collected daily; weekly weights will be collected thereafter. Patients will be instructed to stop administering study drug and contact the Investigator if their daily weight increases as per the criteria outlined in Section 9.1.1. Patients will be provided instructions within the Informed Consent Form to help ensure consistent weight collection throughout the study.

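### For Cohorts 3 and 4 in Part 2, the protocol text requires daily home weights to Week 24, but the Table 6 footnote stops them at Week 20, the visit at which the dose may be raised

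*Protocol*

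**What the plan says.** Three statements in the protocol text set eight weeks for Cohorts 3 and 4 in Part 2:

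- Section 9.1.1, on how long the home scale is used after Week 16: "or eight weeks (Cohorts 3 and 4) of the extension period and will record their weights daily". For Cohorts 1 and 2 the period is four weeks.
- Section 9.10.8, on how long collection stays daily: "or first eight weeks (Cohort 3 and 4) of both Part 1 and Part 2, weights will be collected daily". After that it is weekly. Here too Cohorts 1 and 2 have four weeks.
- Section 9.1.1, on who must stop drug after a five-pound gain: "or 8 weeks (Cohorts 3 and 4) of Part 2 will be instructed to stop taking their study medication immediately". The rule also applies throughout Part 1, and for four weeks of Part 2 in Cohorts 1 and 2.

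Table 6 is the Part 2 schedule for Cohorts 3 and 4. Its footnote e reads: "Weights taken at home by the patient should be taken daily starting at week 16 through and including week 20 and weekly thereafter". Footnote e of Table 5, the Part 2 schedule for Cohorts 1 and 2, has the same wording, and there it agrees with Section 9.1.1.

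On dosing, Section 7.1 states: "All patients in Cohorts 3 and 4 will have the option to up-titrate their dose at the Week 20 visit". Section 7.3 adds: "Dose escalation during the extension period is permitted for all patients at the Week 20 visit only". In Part 1, Table 4 footnote f says that home weights for these cohorts "will begin on Day 2 and should be taken daily for the first 8 weeks and weekly thereafter".

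**The concern.** A site cannot comply with both instructions, and the protocol gives no rule for choosing between text and table. Section 9.10.8 makes this harder: it sends the site to Table 6 for timing and then states eight weeks itself.

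The mismatch concerns a safety instruction. The five-pound rule tells the patient to stop study drug at once, and it can act only when the patient is weighed. A site working from Table 6 drops to weekly home weights just after a possible dose increase, while a site working from Section 9.1.1 does not. Patients could then be monitored differently from site to site, and deviations from the weighing schedule could not be judged consistently.

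Section 9.1.1 also says that patients entering the extension are to be watched for weight gain in the same way as after randomization. For Cohorts 3 and 4, that meant eight weeks of daily weights spanning the dose escalation. Section 5.1.2 explains why frequent weighing matters: in the earlier trial in Stage 4 chronic kidney disease, heart failure on the drug was often preceded by a gain of several kilograms within the first weeks.

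**Working it through.** This is a comparison of text plus day arithmetic.

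**Inputs.** Part 2 starts at the Week 16 visit (Protocol Section 7.1). Target days are Week 4 = Day 28, Week 8 = Day 56 and Week 16 = Day 112 (Protocol Table 4), and Week 20 = Day 140 and Week 24 = Day 168 (SAP Table 1). The footnote's end point can mean the Week 20 visit or the end of that week, so both readings are carried through.

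**Period set by Sections 9.1.1 and 9.10.8.** Week 16 + 8 weeks = Week 24; 168 − 112 = 56 days.

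| Quantity | Ends at Week 20 visit | Ends at close of Week 20 |
|---|---|---|
| Days of daily weights under Table 6 | 140 − 112 = 28 | 28 + 7 = 35 |
| Share of the 56 days | 28/56 = 50% | 35/56 = 62.5% |
| Gap | 56 − 28 = 28 days | 56 − 35 = 21 days |
| Home weights in the gap, daily against weekly | 28 against 4 | 21 against 3 |
| Home weights lost | 24 | 18 |

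The longest interval between scheduled home weights in the gap rises from 1 day to 7.

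**Daily weighing after the escalation visit.**
- Part 1, Table 4 footnote f: Week 4 to Week 8, 56 − 28 = 28 days.
- Part 2, Table 6 footnote e: 0 to 7 days.
- Part 2, Sections 9.1.1 and 9.10.8: Week 20 to Week 24, 168 − 140 = 28 days, the same as Part 1.

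**Which text is in error.** The evidence points to the footnote. Its wording is that of the Cohorts 1 and 2 table. Sections 9.1.1 and 9.10.8 agree with each other and with the Part 1 schedule for these cohorts. The body of Table 6 marks home weight and diary review at every contact from Week 17 to Week 24, including Weeks 21, 22, 23 and 24. Carry-over from Table 5 is an inference, but the contradiction does not depend on it.

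**The case against.** The mismatch is not in dispute. The case against concerns how much it matters, and several of its points stand.

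- **The stop rule already runs on weekly weights elsewhere.** In Part 1 it applies throughout, while daily weighing ends at Week 8 for Cohorts 3 and 4 (8 weeks before Week 16) and at Week 4 for Cohorts 1 and 2 (12 weeks before). Weekly weighing under an active rule is therefore not a failure in itself. Section 9.1.1 also restates the Part 2 rule once without an end date, so 56 days is not the only possible reading of how long the rule lasts. This stands. The difference is that in Part 1 weekly weighing in Cohorts 3 and 4 starts four weeks after escalation, by stated design.
- **Cohorts 1 and 2 do not restart daily weights when they escalate in Part 2.** They get a call at one week and a visit with chemistry and natriuretic peptides at two weeks. Table 6 gives Cohorts 3 and 4 more than that: calls at Weeks 21 and 23, visits at Weeks 22 and 24 with weight, chemistry and BNP, and weekly home weights. This limits the harm.
- **The documented risk period is covered.** Section 5.1.2 reports that the excess risk "appeared to be limited to the first three to four weeks after initiation of treatment", and Table 6 has daily weights for those weeks in placebo patients crossing to active drug. Renewed risk after escalation is inferred from the eight-week rule, not reported.
- **The loss of home weights is what any move from daily to weekly gives:** 6 in 7, or 86% on either reading. Counting home weights alone also leaves out the clinic weights at Weeks 22 and 24.
- **Patients' own instructions are in the consent form,** which is not among these documents. If it says eight weeks, the footnote may have little effect in practice.

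None of this reconciles the two instructions. It lowers the weight of the point.

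**Conclusion.** The concern holds. For Cohorts 3 and 4 in Part 2, Table 6 footnote e contradicts Sections 9.1.1 and 9.10.8 by 3 to 4 weeks of daily weighing, starting at or within a week of the only visit at which the dose may be raised. The intended design is clear from the text, and the footnote departs from it.

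This should be corrected, but it is not a major safety failure: the remaining calls, visits, weekly home weights and symptom reporting still provide monitoring. It has no bearing on randomization or on the efficacy analysis.

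The size rests on target visit days and on the two readings of the footnote's end point. Any Cohort 3 or 4 patient in Part 2 could be affected, chiefly those who up-titrate at Week 20. Their number cannot be derived from the documents. Nor can it be known which instruction sites and patients actually follow.

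**What to change.** In Table 6 footnote e, change the end of daily weighing from Week 20 to Week 24. Leave Sections 9.1.1 and 9.10.8 and Table 5 footnote e as they are.

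The burden is 18 to 24 more home weights per Cohort 3 or 4 patient, counted to the Week 24 visit. No new visit, call or form is needed: patients already have the scale, and Table 6 already dispenses the diary at Weeks 20 and 22 and reviews it at each contact to Week 24.

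Under Section 15.5 the edit has to be a protocol amendment with the usual approvals, at approximately 80 centers. It is cheapest when folded into the next amendment. The consent form's weighing instructions should be checked at the same time. If they repeat the four-week period for these cohorts, the form must be revised too, and Section 15.3 requires affected patients to sign the new version.
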